### 1.2. Study Design

This is a multicenter, open-label, 12-week, safety extension study conducted in China. Participants will be treated with atogepant 60 mg once daily, to be taken on an outpatient basis at approximately 2 centers.

The study will consist of a 12-week treatment period and a 4-week safety follow up period. All participants who complete Study 3101-303-002, and meet all eligibility requirements may participate in this study.

After signing the informed consent, Chinese participants will directly rollover from Study 3101303-002 (Phase 3 CM); hereafter referred to as the lead-in study. As such, participants will have Visit 7 from the lead-in study function as Visit 1 for this extension study (3101-311-002). After Visit 1, study visits will occur every 4 weeks during the 12-week open-label treatment period. A safety follow-up visit will occur 4 weeks after the last dose of atogepant 60 mg in the open-label treatment period.

Note, there may be participants who complete Visit 7 in the lead-in study before this extension study (3101-311-002) has been initiated. Those participants should complete Visit 7/ET and Visit 8/end of study (EOS) Visit (including discontinuation of study intervention) per the lead-in study Schedule of Visits and Procedures.

Depending on the timing of the initiation of this extension study (3101-311-002), in relation to each participant's planned Visit 8 schedule in the lead-in study, Visit 1 for this extension study can be conducted on the same day as Visit 8/EOS Visit for the lead-in study, or soon thereafter.

- If this extension study is initiated prior to the participant's planned Visit 8 in the lead-in study, then Visit 8/EOS Visit in the lead-in study should be conducted on the same day as Visit 1 for this extension study (3101-311-002).
- If this extension study is not initiated prior to the participant's planned Visit 8 in the lead-in study (ie, there is a gap between Visit 8 of the lead-in study and Visit 1 of this extension study), then Visit 8/EOS should be conducted as planned per the lead-in study Schedule of Visits and Procedures. When this extension study is initiated, the participant should return to the clinic as soon as possible, and Visit 1 for this extension study should be conducted per [Table 1-1 Schedule of Visits and Procedures](#).

Participants will return to the clinic for safety assessments at 4, 8, and 12 weeks relative to Visit 1. A safety follow-up visit will occur 4 weeks after the last dose of atogepant 60 mg once daily. For details, please see [Table 1-1 Schedule of Visits and Procedures](#).

The primary objective of the study is to assess the safety and tolerability of treatment with atogepant 60 mg once daily over a 12-week duration for the prevention of migraine in Chinese participants who completed Study 3101-303-002 (CM). The planned safety assessments include collection of AEs, clinical laboratory determinations, ECGs, vital sign measurements, physical examinations, and the C-SSRS.

Table 1-1 Schedule of Visits and Procedures

Study Period	Open-label Treatment Period (12 weeks)				Safety Follow-up Period (4 weeks)
	Visit 1 a	Visit 2	Visit 3	Visit 4	
Week (Day)	Day 1	Week 4 (Day 28)	Week 8 (Day 56)	Week 12 (Day 84)	Week 16 (Day 112)
Visit Windows	N/A	± 3 days	± 3 days	± 3 days	± 3 days
Obtain Informed Consent and participant privacy	X				
Access IWRS	X	X	X	X	X
Assess inclusion/exclusion criteria	X				
Collect medical history b	X				
Perform physical examination	X			X	X
Collect vital sign measurements c	X	X	X	X	X
Perform ECG	X		X	X	
Perform urine pregnancy test d	X	X	X	X	X
Clinical laboratory determinations e	X	X	X	X	X
eDiary instructions and training f	X				
Participant eDiary data collection fg			X		
eDiary data (headache duration, frequency, characteristics and symptoms, acute medication use, AIM-D, activity level and activity limitation) and compliance review h		X	X	X	
MSQ v2.1 (eTablet) ij	X	X	X	X	X
C-SSRS (eTablet) k	X	X	X	X	X
Collect eDiary				X	
Dispense atogepant	X	X	X		
Review atogepant compliance and accountability		X	X	X	
Adverse events				X	
Concomitant medications/concurrent procedures				X	

CM = chronic migraine; C-SSRS = Columbia Suicide Severity Rating Scale; ECG = electrocardiogram; EOS = end of study; ET = early termination; eTablet = electronic tablet; INR = international normalized ratio; IWRS = interactive web response system; WOCBP = women of childbearing potential.

- a After providing informed consent for this study, Visit 1 will be conducted on the same day as Visit 7/Visit 8 of the lead-in study (Study 3101-303-002 [Phase 3 CM]); procedures conducted as part of Visit 7 of the lead-in study should not be repeated. Visit 1 must be conducted in office. All other visits, should be conducted in office unless it is necessary to conduct a remote visits for the safety of participants (eg, COVID-19 or other pandemic): for details please refer to the Remote Visit Schedule of Assessments in the protocol).
- b Medical history will be collected for participants who have a gap between the last visit of the lead-in study and Visit 1 of this extension study and only new medical history during the gap need to be collected.
- c Vital sign measurements: weight, sitting and standing pulse rate, respiratory rate, sitting and standing blood pressure, and body temperature.
- d For WOCBP only, a urine pregnancy test will be performed at all visits.
- e Clinical laboratory determinations include chemistry, hematology, coagulation parameters (INR), and urinalysis to be collected for all visits. Samples for serology and the urine drug screen will be collected only at Visit 1.
- f Participants should begin using the eDiary at Visit 1 and for the duration of the treatment period.
- g Daily eDiary data collection includes: headache frequency, duration, characteristics, symptoms, acute medication use, AIM-D, Activity Level, and Activity Limitation.
- h Participants must bring their eDiary to all visits (except Visit 5).
- i Participant will complete on eTablet.
- j PRO measures should be administered prior to any tests and/or evaluations unless indicated otherwise in the protocol.
- k At all visits, the "Since Last Visit" C-SSRS will be completed for all participants. Clinicians will complete on eTablet.

## 2. Statistical Hypotheses

Since the primary objective of this study is to assess the safety and tolerability of 12 weeks of atogepant treatment, there is no statistical hypothesis specified for the study.

### 3. Sample Size Determination

Chinese participants who complete Study 3101-303-002, and meet all eligibility requirements, may participate in this extension study. Approximately 3 Chinese participants are expected to participate in this extension study. The sample size is different from the sample size planned in the protocol.

#### 4. Populations for Analysis

The analysis populations will consist of participants as defined below.

- The Safety population will consist of all participants who receive at least one dose of the study intervention (atogepant) in this extension study.
- The mITT population will consist of all participants who received at least 1 dose of study intervention (atogepant) in this extension study and had at least 1 evaluable post-baseline 4-week period of eDiary data in this extension study.
- The listing of serious adverse events and participants who died will be provided for the Screened population. The Screened population will consist of all rollover participants from lead-in 3101-303-002, who signed informed consent for the study.

## 5. Statistical Analyses

### 5.1. General Considerations

- Efficacy endpoints will be listed using the mITT population.
- Safety endpoints will be listed using the Safety population.
- Partial dates will be treated as missing in computation or in variable derivation unless specified otherwise, but will be listed in the data listings as they appear on the eCRF.
- The baseline value as defined for the lead-in study will be used as the baseline in this extension study. For monthly endpoints, baseline is defined as assessments during the last 28 days of baseline period in the lead-in study. For efficacy and safety endpoints that are assessed at clinical visits, baseline is defined as the last non-missing efficacy or safety assessment, respectively, before the first dose of study intervention in the lead-in study.
- Study intervention is treatment administered (atogepant 60 mg QD).
- In general, statistical analyses will be performed using SAS version 9.4 or higher
- MedDRA version 24.0 or higher will be used to code adverse events, and medical history
- WHODrug Global B3 (v.202103 or higher) will be used to code medications.

### 5.2. Participant Disposition

The disposition will be listed for participants.

### 5.3. Efficacy Endpoint Analysis and Health Outcome Measures

#### 5.3.1. Definition of Endpoint

Since the primary objective of this open-label extension study is to assess the safety and tolerability of 12 weeks of atogepant treatment, efficacy endpoints are not classified as primary, secondary, or additional.

- The following endpoint will be listed: Change from baseline in monthly migraine days at each monthly period (ie, each consecutive 4-week period)

Other efficacy measures collected, including health outcome endpoints, will be presented in listings.

On a daily basis during the open-label treatment period, participants are to record into an eDiary information on the daily total duration of headache, headache specific characteristics and symptoms, the worst pain severity, and use of any acute headache pain medication. Participants will be able to report headache data, including absence of headache, for the day of the eDiary report and for the day immediately prior to the day of the eDiary report, as long as information reported is for a time subsequent to the participant's most recent report. This is defined as a one-day "missing-recall" window.

Following Visit 1, there are 3 visits at 4-week intervals encompassing a 12-week open-label treatment period of the study and a 4-week safety follow-up period. In practice, there may or may not be exact 4-week durations between two consecutive visits and the visits might not align with each 28-day period recorded in the eDiary (ie, Weeks 1 to 4, 5 to 8 and 9 to 12,

corresponding to Days 1 to 28, 29 to 56, and 57 to 84). Therefore, for monthly data analysis purposes, the number of migraine days will be calculated for consecutive 28-day periods beginning with Day 1, the first dose date of the open-label study intervention.

For more details refer to the Protocol Amendment 1 Sections 6.2 and 6.3.

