#### 5.3.4. Health Outcome Measures

The AIM-D, Activity Level, and Activity Limitation will also be collected daily via an eDiary.

The MSQ v2.1 will be administered in an eTablet at specified visits.

AIM-D and MSQ v2.1 will be listed on mITT population.

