## 6.2. Appendix 2: Changes to Protocol-Planned Analyses

The following changes to the Protocol amendment 1 were made in this SAP:

1. Section 7.2.2 of the protocol amendment 1 stated that “The related health outcome analyses will be documented in the health economics and outcomes research statistical analysis plan.” Instead, these health outcome analyses are added to this SAP document.
2. Removed following efficacy variables:
  - Change from baseline in monthly headache days at each monthly period.
  - Change from baseline in monthly acute medication use days at each monthly period.
  - $\geq 25\%$ ,  $\geq 50\%$ ,  $\geq 75\%$ , and 100% improvement (decrease) in monthly migraine days at each monthly period.
  - Change from baseline in monthly cumulative headache hours at each monthly period
  - Change from baseline in monthly triptan use days at each monthly period
  - Change from baseline in monthly moderate/severe headache days at each monthly period
  - Change from baseline in monthly severe headache days at each monthly period.
  - Other Health Outcome endpoints (see Section 5.3.1)
3. Efficacy variables will be listed, and will not be summarized.
4. Removed following demographic table summaries. Where noted in the body of the SAP, data will be presented in listings:
  - Analysis populations
  - Summary of enrollment category
  - Concomitant medication during the follow-up period
5. Removed following safety summaries. Where noted in the body of the SAP, data will be presented in listings:
  - TEAEs by SOC, PT and severity
  - NEAEs
  - Common ( $\geq 2\%$ ) TEAEs by PT
  - Summary of baseline, post-baseline, and change from baseline in laboratory parameters
  - Summary of baseline, post-baseline, and change from baseline in vital signs
  - Summary of baseline, post-baseline, and change from baseline in ECG

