The monthly migraine days is defined the total number of recorded migraine days in the eDiary divided by the total number of days with eDiary records during each monthly period and multiplied by 28. The baseline value as defined for the lead-in study will be used as the baseline in this extension study. For each postbaseline 4-week treatment period, a minimum of 14 days’ eDiary data during that period is required for the migraine days to be evaluable. If a participant does not have at least 14 days of diary data for a monthly treatment period, the migraine days for that period will be considered as missing. Migraine days will be derived for each participant at baseline and for each postbaseline monthly treatment period (Weeks 1-4, 5-8, 9-12). The same method to derive monthly migraine days will be used to derive monthly headache days, monthly acute medication use days, monthly triptan use days, monthly cumulative headache hours, monthly headache day pain intensity, monthly moderate/severe headache days, and monthly severe headache days.

If a subject reports ‘Yes’ to the intake of allowed medication(s) to treat an acute migraine but does not list any of them in the diary, then the acute medication use days will not be counted in this situation.

Subsequent to Day 1, the number of headache days will be counted in successive and non-overlapping 4-week (ie, 28-day) windows. Headaches that continue into a subsequent 4-week period will be counted (with recorded severity and duration) as occurring in each period.

If any postbaseline eDiary window for a participant has at least 14 but less than 28 days of reported data, the prorated approach will be used. If a participant reports less than 14 days of headache data, the participant's observed counts in that particular 28-day eDiary window will be set to missing for that window. These prorating rules will be applied to all efficacy analyses of eDiary data unless otherwise stated.

Monthly efficacy endpoints are defined in a prorated fashion. For example, monthly migraine days are defined as the total number of recorded migraine days in the eDiary divided by the total number of days with eDiary records during each monthly period and multiplied by 28.

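### SAP Appendix 2 and Section 5.3.1 leave the reporting status of 9 to 15 of the 16 protocol endpoints unclear, and the named laboratory listing set omits INR and urine glucose and protein

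*SAP*

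**What the plan says.** **Efficacy and health outcomes.** Protocol 7.2.1 has eight efficacy endpoints and protocol 7.2.2 has eight health outcome endpoints. SAP 5.3.1 names one endpoint for listing, change from baseline in monthly migraine days, and adds: "Other efficacy measures collected, including health outcome endpoints, will be presented in listings". SAP 5.3.4 states: "AIM-D and MSQ v2.1 will be listed on mITT population".

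SAP 6.2 (Appendix 2) records the changes from the protocol:

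- Item 1, on health outcomes: "Instead, these health outcome analyses are added to this SAP document".
- Item 2: "Removed following efficacy variables", followed by the other seven protocol efficacy endpoints and a last bullet, "Other Health Outcome endpoints (see Section 5.3.1" (closing bracket omitted here).
- Item 3: "Efficacy variables will be listed, and will not be summarized".
- Item 5: "Removed following safety summaries. Where noted in the body of the SAP, data will be presented in listings". Item 4 (demographic tables) has the same rider. Item 2 has none.

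The derivation section, SAP 6.4.2.1, still says: "The same method to derive monthly migraine days will be used to derive monthly headache days, monthly acute medication use days", and continues through the remaining diary counts. SAP 6.4.3 keeps scoring rules for AIM-D, the two Activity items and MSQ.

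**Laboratory data.** SAP 5.4.4.1 ties the laboratory listing to a table with three rows: chemistry, hematology and urinalysis, the last with only specific gravity and pH. Protocol Table 6-1 also has a coagulation row (INR) and a fuller urinalysis row. Footnote e of the visit schedule in both documents has INR collected at all visits.

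**The concern.** When a plan moves from tables to listings, the reader needs to know which variables are listed, in what form, and which are dropped. Here the appendix that should record this sends the reader to a section that says something else.

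A programmer who follows Appendix 2 item 2 and the single efficacy endpoint shown in SAP 1.1 could deliver monthly migraine days alone. One who follows 5.3.1 and 6.4 could deliver up to all 16 endpoints. Two of the three efficacy endpoints that the protocol summary names, monthly headache days and the 50% responder endpoint, are on the removed list.

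For safety, which is the primary objective, 5.4.4.1 taken as written gives a laboratory listing without a parameter that is measured at every visit.

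**Working it through.** The documents state no figure to reproduce, so the check is a count and a comparison of sections.

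**Step 1. Endpoints in the protocol.** Section 7.2.1: 8 efficacy endpoints, with the four responder thresholds counted as one. Section 7.2.2: 3 MSQ + 3 AIM-D + 2 Activity = 8. Total 8 + 8 = 16.

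**Step 2. Endpoints on the removed list.** Item 2 names 7 of the 8 efficacy endpoints. The number of health outcome endpoints depends on the word *Other*:

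| Reading of *Other Health Outcome endpoints* | Health outcomes | Total unclear |
|---|---|---|
| All eight | 8 | 7 + 8 = 15 of 16 |
| Those not named for listing in SAP 5.3.4 (Activity Level, Activity Limitation) | 2 | 7 + 2 = 9 of 16 |

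Counting the four responder thresholds separately adds 3 to each figure: 12 to 18 of 19.

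**Step 3. How firm the conflict is.**

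- *Health outcomes.* Item 1 adds them, item 2 removes some or all of them, and 5.3.1, to which item 2 refers, lists them. Section 5.3.1 speaks of endpoints, which protocol 7.2.2 defines as changes from baseline. A reading in which only raw data are listed therefore fits poorly.
- *Seven efficacy variables.* Item 2 removes variables; 5.3.1 lists measures collected. One can reconcile these by listing the diary data and dropping the derived change and responder variables. Item 3 and the retained derivations point the other way. The text is ambiguous.

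**Step 4. What is still derived.** Of the upper-bound 15 endpoints:

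- 9 have a derivation rule: 6 diary counts in 6.4.2.1 and 3 MSQ domains in 6.4.3.
- 5 are only partly covered. AIM-D (3) and Activity (2) have monthly scores, but no rule for the 12-week average that protocol 7.2.2 includes.
- 1, the responder endpoint, has no rule.

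Check: 9 + 5 + 1 = 15. Among the seven efficacy variables, 6 of 7 are still derived.

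**Step 5. Laboratory set.**

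| Parameter | Protocol Table 6-1 | SAP 5.4.4.1 set | SAP Table 6-3 PCS criterion |
|---|---|---|---|
| INR | yes | no | no |
| Urine glucose | yes | no | yes |
| Urine protein | yes | no | yes |

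Urine glucose and protein would reach the PCS listing if a value met the criterion. INR has neither route. The schedule gives up to 5 INR results per participant (Visits 1 to 5), and possibly fewer drawn in this study, because lead-in Visit 7 procedures are not repeated. Two general statements could cover INR: SAP 5.1, that safety endpoints are listed, and SAP 6.4.4, that all assessments appear in the data listings.

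**The case against.** The best defence is that the intent is clear. The SAP change history says summary tables were removed in favour of listings because few participants were expected, and that health outcome endpoints were brought in from the protocol. Item 3 agrees, and the last bullet of item 2 sends the reader to a section that promises listings. On this view item 2 is loosely worded and means *no longer summarized*. That is probably what was meant, and it is why the point is minor. But the SAP does not say it: items 4 and 5 speak of summaries and carry the listing rider, while item 2 speaks of variables and does not.

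The defence also limits three stronger readings that a reader might infer.

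- *That 15 of 16 endpoints are flatly contradictory.* Fifteen is an upper bound. Section 5.3.4 commits to listing AIM-D and MSQ, and a compatible reading exists for the seven efficacy variables.
- *That INR has no listing at all.* SAP 5.1 and 6.4.4 would cover it if read generally, and SAP Section 1 places listing specifications in a separate document not available here. What can be said is that no listing names INR and the 5.4.4.1 set leaves it out.
- *That results bearing on liver safety would be lost.* INR is part of one of the five discontinuation criteria in protocol 9.5, but that criterion also requires ALT or AST at or above 3 x ULN. Such participants fall under the additional liver listings in SAP 5.4.4.1, which include liver laboratory tests performed.

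The omission of urine glucose and protein, despite their PCS criteria, may mean the 5.4.4.1 table was not intended as a closed list. That supports a general reference to the protocol table over adding INR alone.

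**Conclusion.** The SAP does not give a single status to between 9 and 15 of the 16 protocol endpoints; the range turns on one undefined word. The conflict is plain for the health outcomes and an ambiguity for the seven efficacy variables. The laboratory set in 5.4.4.1 omits INR, urine glucose and urine protein, and only general wording elsewhere would bring INR in.

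The severity is minor. About 3 participants are expected, the SAP has no hypothesis and the protocol plans no inferential efficacy analysis, so no test, error rate or estimate is affected. What is affected is completeness of reporting. Because the study is open-label, one might suspect that endpoints could be chosen after values are seen. The documents do not support that as a finding, since 5.3.1 promises listings of the other measures.

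This rests on the SAP text as it stands. The separate specifications may already settle the format, but which protocol endpoints and parameters are reported should be fixed in the SAP.

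**What to change.** Before database lock:

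1. In SAP 5.4.4.1, replace the named set with a reference to the full parameter list in protocol Table 6-1, so that INR and the remaining urinalysis parameters are listed.
2. In Appendix 2 item 2, say that the named variables and the health outcome endpoints are no longer summarized but are listed under 5.3.1. If any is truly dropped, name it and delete its derivation in 6.4.2.1 or 6.4.3. Replace *Other* with the endpoints meant.
3. For endpoints kept as derived values, add the responder rule and the 12-week average rule for AIM-D and the Activity items.

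The cost is SAP wording and a few extra listing columns from data already collected. No participants, procedures or objectives change.

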### 5.3.2. Main Analytical Approach

Migraine days will be listed based on the mITT population.

### 5.3.3. Key Efficacy Measures

**A migraine day** is defined as any calendar day on which a headache occurs which meets criteria A, B, and C OR meets criteria D and E, as listed below, as per participant eDiary. Calendar days begin at midnight and last until 11:59 PM (23:59).

- A. Headache has at least two of the following four characteristics:
  - i. Unilateral location
  - ii. Pulsating quality
  - iii. Moderate or severe pain intensity
  - iv. Aggravated by or causing avoidance of routine physical activity (eg, walking or climbing stairs)
- B. At least one of the following:
  - i. Nausea and/or vomiting
  - ii. Photophobia and phonophobia
  - iii. Typical aura (ie, visual, sensory, or speech/language) accompanying or within 60 minutes before headache begins
- C. Duration of headache lasting 2 hours or longer on a calendar day unless an acute, migraine-specific medication (ie, triptan or ergot derivative) was used after the start of the headache, in which case no minimum duration will be specified.

OR

- D. Any headache which fulfills one criterion from (1) and at least one criterion from (2) OR fulfills at least two criteria from (1) and no criteria from (2).
  - 1) Headache characteristics:
    - i. Unilateral location
    - ii. Pulsating quality
    - iii. Moderate or severe pain intensity
    - iv. Aggravated by or causing avoidance of routine physical activity (eg, walking or climbing stairs)
  - 2) Symptoms:
    - i. Nausea and/or vomiting
    - ii. Photophobia and phonophobia
    - iii. Typical aura (ie, visual, sensory, or speech/language) accompanying or within 60 minutes before headache begins

B. Duration of headache lasting 2 hours or longer on a calendar day unless an acute, migraine-specific medication (ie, triptan or ergot derivative) was used after the start of the headache, in which case no minimum duration will be specified.

**A headache day** is defined as any calendar day on which headache pain lasting 2 hours or longer occurs unless an acute headache medication (eg, ibuprofen, triptan) was used after the start of the headache, in which case no minimum duration will be specified. Note that antiemetics will not be counted as an acute headache medication for headache day identification. Calendar days begin at midnight and last until 11:59 PM (23:59).

**An acute medication use day** is defined as any day on which a participant reports, per eDiary, the intake of allowed medication(s) to treat an acute migraine. The allowed medications include the following categories of drugs: triptans, ergots, opioids, analgesics (including acetaminophen), NSAIDs (including aspirin), and antiemetics.

**A triptan use day** is defined as any day on which a participant reports intake of a triptan to treat a migraine per eDiary.

Headache day pain intensity is defined as the worst pain intensity on any headache day where headache pain intensity will be subjectively rated by the patient on a scale from mild to severe:

- Mild pain (=1)
- Moderate pain (=2)
- Severe pain (=3)

If participants experience no headache in a day, then the corresponding pain intensity of that day will be set as missing.

